#### **8.2.7.1 Signs and symptoms of vaginal atrophy**

The symptoms evaluated will be the following:

- Vaginal dryness
- Pruritus or itching
- Dyspareunia

Each symptom will be scored in a numeric scale from 0 to 3, as shown below:

- 0 Absence. The symptom is not present
- 1 The symptom is of mild intensity, without interfering in the patient's activity
- 2 The symptom is of moderate intensity, causing obvious discomfort to the patient
- 3 The symptom is stated as very irritating and severe in intensity

A Global Symptoms Score will be evaluated. It will be calculated by summing the intensities of all the three symptoms of vaginal atrophy in a certain time point, thus ranging between 0 and 9. The variation in the Global Symptom Score vs baseline will be assessed at weeks 3 and 12.

The signs evaluated will be the following:

- Vaginal mucosa with flattening of folds or thinning
- Dryness of the mucosa
- Fragility of the mucosa

Each one of these signs will be scored by the investigator on a numerical scale in accordance with their presence and degree of severity as follows:

- 0 Absence. The sign is not present.
- 1 The sign is present and is considered a mild alteration
- 2 The sign is present and is considered a moderate alteration
- 3 The sign is present and is considered a severe alteration

#### **8.2.7.2 Vaginal Maturation value and pH**

The averages of the differences between the baseline and the final MV and pH of the 0.005% Estriol vaginal gel and placebo groups will be shared by a non-parametric test., to determine the possible superiority of the 0.005% Estriol vaginal gel treatment compared with placebo administration.

These same tests will be used to analyse the change in the MV and pH after the initial observation period of 3 weeks.

All of the above secondary analyses will be conducted at a two-sided 0.05 level of significance.

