## 6.4 Efficacy assessments

The following assessments will be performed at baseline, week 3 (day 22 +/- 3 days) and week 12 (day 85 +/- 3 days) or early withdrawal visit.

- Symptoms of vaginal atrophy (vaginal dryness, dyspareunia and pruritus).
- Signs of vaginal atrophy (mucosa with thinning or flattening of folds, dryness or fragility of the vaginal mucosa).
- Measurement of vaginal pH on the vaginal secretion using a reactive strip (pH 2.0 - 9.0, provided by the sponsor). The investigator team will insert the strips in the vagina and will moisten them as much as possible with the vaginal wall secretion. Then, when the strip is coloured, the investigator will check the combination of colours on the strip and check the pH value to which it corresponds, recording this value in the eCRF. The reading should be made whilst the strip is still damp. The strips will be discarded once the pH has been recorded in the eCRF.
- Vaginal cytology sample to evaluate the vaginal Maturation Value. Two smears (with two different spatulas provided by the sponsor one to take the sample and the other to take the countersample) will be made per patient (sample and countersample), which will be obtained from the bottom of the right and left vaginal sac respectively. Each smear will be suitably labelled. The vaginal smears will be fixed whilst they are still moist with a water-soluble fixation spray for cytodiagnosis (provided by the sponsor). The cytologic samples will be sent to central laboratory (full instructions will be given in a laboratory manual). For the cytologic evaluation, the number of parabasal, intermediate and superficial cells will be calculated in duplicate on 100 consecutive cells of vaginal cytology. The average of the two percentages obtained for each cell type will be calculated, which will serve to determine the maturation value (MV) based on the following formula:

$$0.2 \times (\% \text{ parabasal}) + 0.6 \times (\% \text{ intermediate}) + 1.0 \times (\% \text{ superficial}).$$

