## 8. Sample Size and Statistical Methods

### 8.1 Determination of Sample Size

This is an exploratory study and there are scarce data to allow a precise sample size calculation. The most relevant data come from Pfeiler(16) who reported that the levels of FSH in patients treated with aromatase inhibitors fell from a mean value of 75.7 to 66.0 mIU/ml after two weeks of daily vaginal treatment with 0,5 g of estriol. Although no figures are reported of the variability of those measurements, an estimation of the standard deviation can be made applying the standard rule of  $[sd = \text{range}/4]$ . The reported range of FSH values in that report is 45.6 – 134.6, thus a reasonable approximation to the sd is  $89/4 = 22.3$ . Under these assumptions, it can be calculated that a sample size of 44 would provide 80% power to detect with an  $\alpha=0.05$  a decrease of FSH levels from 75.7 to 66.0 mIU/ml assuming a standard deviation of 22.3.

The hormone levels in women treated with IA who are not receiving estrogen therapy are likely to suffer physiological temporal oscillations. These variations could make difficult the interpretation of any eventual modification of hormone levels observed in the estriol treated women. In the absence of data of naturally occurring variations in hormone levels of women treated with IA that allow us to interpret the results of hormone determinations under study, it is considered appropriate to include a placebo group to provide reference data. In this case, the placebo is a vaginal moisturizing gel.

It is estimated that a group of 11 women will allow the assessment of physiological fluctuations in hormone levels. Additionally, this sample size for the placebo group will provide 80% power and  $\alpha=0.05$  to differentiate between active and placebo (ratio 4:1) on the change in the vaginal maturation value, which is a secondary variable of the study that provides objective information about the effectiveness of treatment on vaginal atrophy (calculation based on the parameter data from the pivotal Blissel study and considering only the subgroup of women who had severe vaginal dryness: change VM active group 24.9 vs 0.6 points in placebo group, SD = 24.2).

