### **8.2.6. Hormone levels**

All these analysis will be based on the ITT population.

The primary endpoint and one of the secondary endpoints are to evaluate the variation from baseline of FSH, LH, estriol, estradiol and estrone blood levels in patients treated with 0.005% estriol vaginal gel/placebo.

The variation of the levels of FSH, estriol, estradiol, estrone and LH after treatment with 0.005% estriol vaginal gel will be studied in each woman. The variation of levels between two arms will be analyzed using a non-parametric test (Mann-Whitney-Wilcoxon test) or an ANCOVA (if it must be adjusted by initial value).

Two determinations of FSH and LH before treatment with 0.005% estriol vaginal gel will be studied in each woman in order to study the intra-individual variation. Screening and baseline determinations will be used for this purpose.

Changes in hormone levels will be studied in each woman along the treatment (see sections 6.1 and 6.2).

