### **8.2.7. Efficacy**

The efficacy analysis will be evaluated in the ITT population.

The primary endpoint, the variation of FSH between week12 and baseline and comparing by arm will be analyzed using a non-parametric test (Mann-Whitney-Wilcoxon test).

An ANCOVA analysis will be used to corroborate the results obtained for the primary endpoint. The ANCOVA analysis will compare the variation of FSH 12 weeks adjusted by FSH basal between the two arms. This analysis will be performed if the relation between FSH 12 and FSH basal is lineal.

The variations in the intensities for each one of the symptoms and signs of the vaginal atrophy, after 3 and 12 weeks, in each treatment arm, will be compared using the non-parametric test Mann-Whitney-Wilcoxon.

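### Maturation value, pH, symptoms and signs are compared between arms as change scores without baseline adjustment: an avoidable loss of precision on secondary endpoints, not an error of validity

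*Protocol*

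**What the plan says.** - **Maturation value and pH** (Protocol 8.2.7.2): the quantity compared is "The averages of the differences between the baseline and the final MV and pH of the 0.005% Estriol vaginal gel and placebo groups". The test is non-parametric, the same tests are used at week 3, and the level is two-sided 0.05.
- **Symptoms and signs** (Protocol 8.2.7): "The variations in the intensities for each one of the symptoms and signs of the vaginal atrophy", at weeks 3 and 12, "will be compared using the non-parametric test Mann-Whitney-Wilcoxon". Section 8.2.7.1 adds a Global Symptoms Score (0 to 9), assessed as variation from baseline, with no test of its own named.
- **Baseline values are collected** (Protocol 6.4): "The following assessments will be performed at baseline, week 3" and week 12, covering symptoms, signs, pH and maturation value.
- **Adjustment is planned elsewhere.** For hormones, section 8.2.6 names Mann-Whitney "or an ANCOVA (if it must be adjusted by initial value"). For FSH at week 12, section 8.2.7 adds ANCOVA on baseline FSH as corroboration, provided the relation is linear. No reason is given for leaving the other outcomes unadjusted.
- **Power** (Protocol 8.1): with 11 placebo women, "this sample size for the placebo group will provide 80% power" at alpha 0.05 "to differentiate between active and placebo (ratio 4:1) on the change in the vaginal maturation value", from "change VM active group 24.9 vs 0.6 points in placebo group, SD = 24.2".

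**The concern.** A change score subtracts the baseline but usually stays correlated with it. A woman who starts with a low maturation value, or with dryness at grade 3 rather than 2, has more room to improve, and entry admits both moderate and severe dryness. Part of any chance difference between arms at baseline therefore reappears in the comparison of changes, and variation that baseline could explain stays in the error term.

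Maturation value is where this matters most. It is the only between-arm comparison with a stated power, and that power is part of the support for a placebo group of 11. The FSH calculation is a before-after one in 44 women, and section 8.1 says separating the arms on the subjective parameters would need a noticeably larger sample.

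**Working it through.** **Inputs.** From section 8.1: difference in change 24.9 − 0.6 = 24.3; SD 24.2, read as the SD of change because it stands beside the changes; 44 and 11 evaluable women. Two-sided 0.05 is from 8.2.7.2. Not in the protocol, so assumed over a range: the correlation rho between baseline and week 12, and k, the baseline SD divided by the follow-up SD.

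**1. The plan's own figure.** Placebo n at 4:1 = 1.25 × (24.2 × (1.960 + 0.842) / 24.3)² = 9.73. Dividing by 0.955, the efficiency of Mann-Whitney relative to the t-test for normal data, gives 10.19, so 11. At 44 and 11, power is 83.3% for a t-test on change and about 80% for a simulated Mann-Whitney test. The stated 11 and 80% both reproduce.

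**2. Effect of adjustment.** Residual variance under ANCOVA, relative to the variance of change, is

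(1 − rho²) / (1 + k² − 2·rho·k).

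With equal SDs (k = 1) this is (1 + rho)/2: 0.65, 0.75, 0.85 and 0.90 for rho 0.3, 0.5, 0.7 and 0.8. When k equals rho it is exactly 1, and adjustment removes no variance.

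**3. Simulated power.** Normal data, linear relation with baseline, SD of change held at 24.2, 6,000 trials per row:

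| k | rho | variance ratio | Mann-Whitney on change | rank ANCOVA (Quade) | ANCOVA |
|---|---|---|---|---|---|
| 1.0 | 0.3 | 0.65 | 80% | 93% | 95% |
| 1.0 | 0.5 | 0.75 | 80% | 89% | 91% |
| 1.0 | 0.7 | 0.85 | 81% | 84% | 89% |
| 1.0 | 0.8 | 0.90 | 80% | 80% | 86% |
| 0.7 | 0.3 | 0.85 | 81% | 86% | 89% |
| 0.7 | 0.7 | 1.00 | 81% | 78% | 83% |
| 0.5 | 0.3 | 0.96 | 80% | 81% | 84% |
| 0.5 | 0.5 | 1.00 | 80% | 79% | 82% |
| 0.5 | 0.8 | 0.80 | 80% | 84% | 89% |

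About 3 points of each ANCOVA gain come from using a normal-theory test on normal data (the t-test on change already has about 83%). The rest comes from the baseline. With no treatment effect and equal SDs, all three methods reject at 4.6% to 5.2%.

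**4. Which k and rho are plausible.** The formula in 6.4 bounds maturation value between 0.2 × 100 = 20 and 100, so a single-visit SD cannot exceed 40. With equal SDs, the single-visit SD is 24.2 / sqrt(2(1 − rho)): 20.5, 24.2, 31.2 and 38.3 for rho 0.3, 0.5, 0.7 and 0.8. The highest correlations therefore fit poorly with equal SDs. Equal SDs are themselves not assured: women on an aromatase inhibitor with moderate to severe dryness may cluster near the floor at baseline, which would make k less than 1.

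**5. Baseline imbalance.** With equal SDs, change regresses on baseline with slope −(1 − rho), so 0.7 to 0.3 of a chance baseline difference carries into the change for rho 0.3 to 0.7. For dryness, if half the women are severe at entry (an assumption), the SE of the difference in the share severe is sqrt(0.25/44 + 0.25/11) = 0.169. The chance of a gap of 20 points or more is then 2 × (1 − Φ(0.20/0.169)) ≈ 0.24.

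**The case against.** The strongest reply is that nothing the plan promises is missed. The planned test reaches its stated 80% with 11 placebo women, randomisation protects its type I error, and this is a secondary endpoint of a study that calls itself exploratory. That stands, and it sets the level of the point.

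A reader might infer from the equal-SD results that the plan gives up a fixed amount of power, with a gain of about 4 points as the least to expect. The protocol does not support that, since it states neither rho nor k. When k is close to rho the baseline explains nothing extra, and rank ANCOVA can fall about 3 points below the planned test. So replacing the planned test with rank ANCOVA, which would keep the analysis non-parametric, is not a safe improvement. ANCOVA did not lose power in any setting examined, though its smallest gains reflect the normal-theory test rather than the baseline.

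A reader might also infer that the baseline is ignored, or that baseline differences pass in full into the result. Neither holds: a change score subtracts the baseline, and only part of a chance difference carries over.

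A non-parametric test is a reasonable choice for a bounded index and a strip-read pH, and the protocol makes its FSH ANCOVA conditional on linearity. That argues for keeping the planned test as a sensitivity analysis, not against adjusting. Finally, a stratified Mann-Whitney (van Elteren) by baseline grade would spread 11 placebo women over up to four grades, and strata without placebo women contribute nothing, so it is a poor remedy for symptoms and signs.

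**Conclusion.** The point holds as an inexpensive gain in precision. Sections 8.2.7 and 8.2.7.2 themselves fix the unadjusted tests, so this is a stated choice and not a detail left open.

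For maturation value, ANCOVA would raise power from about 80% to between about 95% and 86% for rho 0.3 to 0.8 with equal SDs. If the baseline SD is 0.5 to 0.7 of the follow-up SD, the gain is about 2 to 10 points. These figures assume that 24.2 is the SD of change, that the data are roughly normal and that the relation with baseline is linear. For pH, symptoms and signs the protocol gives no inputs, so no gain can be stated. The case there rests on the general argument and on consistency with the hormone analyses.

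**What to change.** - **8.2.7.2:** make ANCOVA of the week-3 and week-12 maturation value and pH, on treatment and baseline value, the main comparison. Report the adjusted difference with its 95% CI. Keep the planned non-parametric test on change as the sensitivity analysis.
- **8.2.7 and 8.2.7.1:** analyse each symptom and sign score, and the Global Symptoms Score, with a model that has the baseline score as a covariate, such as ANCOVA or proportional odds. Keep Mann-Whitney on change as sensitivity.
- **Timing:** fix the choice before unblinding. Section 8.2.1 lets the SAP modify the protocol's plans and requires an amendment only for major changes to the primary endpoint or its analysis, so SAP wording may suffice.

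The cost is wording and minor programming, with no new data or patients. Statistically it costs one degree of freedom and an assumption of a roughly linear relation with baseline, which the retained non-parametric test helps to check.

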#### **8.2.8. Safety Analyses**

The toxicity and tolerability of the study drug will be evaluated in the safety population. Safety analyses will include summaries of the incidence of adverse events by MedDRA that occur during the study treatment period or within 30 days (+/- 5 days) of the last dose of study treatment, regardless of causality and according to the relationship to study drug as assessed by the investigator. Additionally, the following safety-related outcomes will be summarized:

- study treatment discontinuations due to adverse events.
- deaths
- SAEs
- hospitalizations and transfusions
- use of key concomitant medications or growth factors.

Analyses for data with discrete dates, for example, deaths, transfusions, and concomitant medications, will be done through 30 days after each patient's last dose of study treatment. Adverse events will also be analyzed in this timeframe; that is, if an event starts within 30 days of discontinuation from study treatment, but after 30 days after the last dose of study treatment, it will not be included.

Adverse events data and serious adverse events will be presented in frequency tables by grade. Hematological and clinical biochemistry toxicities will be assessed from laboratory test parameters. The safety analysis will be performed in the safety population.

Adverse events data and serious adverse events will be reported in frequency tables (overall and by grades). Adverse events will be compared using the chi-square tests (Fisher's Exact test in the case of observing frequencies <5%).

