#### ➤ Safety Analyses

Adverse events data and serious adverse events will be reported in frequency tables (overall and by grades). The safety analysis will be performed in the population that has received at least one dose of the drug. AEs will be graded according to MedDRA. Adverse events will be compared using the chi-square tests (Fisher's Exact test in the case of observing frequencies <5%).

Symptoms of Vaginal atrophy will be evaluated with a codification from 0 to 3.

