### 3. Investigational Plan

#### 3.1 Study Design

This is a phase II, prospective, randomized, double-blind, placebo-controlled, international (Spain and Sweden) and multicentre study.

Sixty patients will be randomized (stratified by site) to receive 0.005% estriol vaginal gel (arm A) and placebo moisturizing gel (arm B) in a 4:1 proportion, so 48 patients will enter in arm A and 12 in arm B. Patients will undergo gynaecological tests, plasma and serum extraction for hormone determinations, adverse events collection and will answer a questionnaire according to what is outlined in Figure 1.

A) Patients randomized to Arm A (experimental arm) will receive:

Investigational drug product: 0.005% estriol vaginal gel (Blissel®)

Route: Vaginal. Administration by an applicator inserted deep inside the vagina

Dose: 1 g of gel, containing 50 µg of estriol

Dosage schedule: Weeks 1-3: single daily application  
Weeks 4-12: twice weekly administration.

[figure not shown]
Women will be instructed to administer the gel at bedtime.

B) Patients randomized to Arm B (control arm) will receive:

Placebo moisturizing gel (vehicle of Blissel®).

Same route and dose schedule than Blissel®.

**Figure1.** Study Design

[figure not shown]

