The differentiation between active and placebo in the subjective parameters of efficacy (secondary) would be possible at the expense of a sample size noticeably superior. Since the evaluation of effectiveness is not primary but secondary in this study, it is not justified in this study to increase the sample for this reason.

In accordance with the above, the study would include 55 women. 44 will receive vaginal estriol gel and 11 with the placebo moisturizing gel). Taking into account 10% of dropouts, the sample to be considered is of 60 women (48 vaginal estriol gel and 12 placebo moisturizing gel). This is an unbalanced study but with an active: placebo ratio of 4:1, which will support an adequate patient randomization (blocks of 5).

10 additional women will be recruited in a first safety phase of the study (8 with vaginal estriol gel and 2 placebo moisturizing gel).

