#### 8.2.1.1 Patient Populations

**Intent to treat population (ITT):** The ITT population will include all patients who are randomized, with study treatment (Estriol gel vaginal 0.005% or placebo) assignment designated according to initial randomization.

The ITT population will be the primary population for evaluating patient characteristics, hormone levels, efficacy and the FSFI questionnaire.

**Per-protocol population:** a subset of the ITT population that received at least one dose of study drug and completed the study without any major protocol violations.

**Safety population:** will include all patients randomized in the study who received at least one dose of treatment, and they will be analyzed according to the actual treatment received. This population is for the safety analysis.

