### **8.2.3. Patient Characteristics**

Patient characteristics could include a summary of the following:

- patients demographics
- time of menopause
- baseline disease characteristics
- preexisting conditions/secondary conditions
- prior therapy

Other patient characteristics will be summarized as deemed appropriate.

The categorical variables will be summarized by contingency tables. The continuous variables will be described by the number of patients with valid values (n), mean, standard deviation, median and range in both arms.

The significance level of all statistical tests is established at 0.05.

The effect of the treatment on continuous variables will be assessed by paired-t analysis (or Mann-Whitney-Wilcoxon in case of lack of normality). Categorical variables will be analyzed by chi-cuadrado or Fisher's exact test.

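### The adverse-event test rule switches to Fisher's exact test on an undefined observed frequency below 5%, not on expected cell counts below 5, so uncorrected chi-square can be applied to very sparse 48-versus-12 tables

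*Protocol*

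**What the plan says.** Protocol section 8.2.8 (Safety Analyses) compares adverse events by chi-square and moves to Fisher's exact test "in the case of observing frequencies <5", where the 5 carries a percent sign. The Safety Analyses paragraph of the protocol summary repeats the trigger: "Fisher's Exact test in the case of observing frequencies <5", again per cent. Neither place says whether the percentage is taken over all women, within an arm or per table cell, and neither mentions expected counts. Section 8.2.3 adds only that "Categorical variables will be analyzed by chi-cuadrado or Fisher's exact test", without a trigger.

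The tables concerned are small and unbalanced. Section 3.1 randomises 60 women, "so 48 patients will enter in arm A and 12 in arm B". The safety population in section 8.2.1.1 "will include all patients randomized in the study who received at least one dose of treatment". Section 8.2.3 sets the level: "The significance level of all statistical tests is established at 0.05".

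**The concern.** The large-sample approximation behind chi-square becomes unreliable when expected cell counts are small, and the customary guard is an expected count below 5. An observed frequency below 5% is a different quantity. With a 12-woman arm, an event can be well above 5% overall and still have an expected placebo count below 1. The written rule therefore sends to chi-square most of the tables that the customary guard would send to Fisher.

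The undefined denominator is a second fault: two statisticians could apply different tests to the same table and both be following the protocol. At stake are individual adverse-event p-values in a trial whose title makes safety its purpose. Some cross 0.05 only because of the test chosen.

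**Working it through.** **Inputs.** Arms of 48 and 12 (section 3.1). These follow from 44 + 11 = 55 women, raised to 60 for dropout at an "active: placebo ratio of 4:1" (section 8.1): 60 × 4/5 = 48 and 60 × 1/5 = 12. The protocol attaches no figure to the test rule, so there is none to reproduce. Assumptions: all 60 women are treated; chi-square is the uncorrected Pearson test; the level is two-sided 0.05 (two-sided is stated only for the secondary analyses in section 8.2.7.2); the true event rate is equal in both arms and between 3% and 40%, since the protocol gives no rates.

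**Step 1: expected counts.** With m events in total, the expected number of placebo women with the event is m × 12/60 = m/5, which is below 5 when m < 25. The expected number without it is (60 − m)/5, below 5 when m > 35. An expected-count rule would thus allow chi-square only for 25 to 35 events.

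**Step 2: smallest expected placebo count at which the written rule still uses chi-square.**
- Pooled (5% of 60 = 3 events): 3 × 12/60 = 0.6.
- Per arm (Fisher if either arm is below 5%): at least 3 of 48 and 1 of 12, so 4 × 12/60 = 0.8.
- Per cell as a share of 60: at least 3 in each event cell, so 6 × 12/60 = 1.2.

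**Step 3: single tables.** For 1/48 versus 2/12, Pearson's statistic is 60 × (1×10 − 2×47)² / (48 × 12 × 3 × 57) = 423,360/98,496 = 4.30, p = 0.038. Fisher gives [C(12,2)×48 + C(12,3)] / C(60,3) = (3,168 + 220)/34,220 = 0.099. That is also chi-square's exact rejection probability given 3 events: 9.9%, all of it placebo excess. This table reaches chi-square only on the pooled reading, because 1/48 is 2.1%.

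The table 5/48 versus 4/12 reaches chi-square on all three readings: p = 0.047, against 0.069 by Fisher. So does 9/48 versus 6/12: 0.025 against 0.056.

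**Step 4: rejection rates.** All 49 × 13 tables were enumerated and weighted by their binomial probabilities. The nominal rate is 2.5% per tail.

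| True rate, both arms | Written rule, pooled: placebo excess | Written rule, pooled: estriol excess | Total | Fisher always: placebo excess |
|---|---|---|---|---|
| 5% | 4.17% | 0.00% | 4.17% | 2.03% |
| 10% | 3.81% | 0.02% | 3.83% | 2.60% |
| 20% | 3.45% | 1.05% | 4.50% | 1.95% |
| 40% | 2.91% | 2.40% | 5.31% | 2.06% |

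Over 3-40% the placebo-excess tail is 2.9-4.2% on the pooled reading and 1.4-2.6% with Fisher. On the per-arm reading it is 1.4-3.6%: 1.42% at a 3% rate, 2.04% at 5%, 3.03% at 10%, 3.58% at 15% and 3.44% at 20%.

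**Step 5: direction of disagreement.** From 3 to 12 events, the tables significant by chi-square but not by Fisher are 1/48 v 2/12, 5/48 v 4/12 and 7/48 v 5/12, all placebo excess. From 13 events they go both ways: 13/48 versus 0/12 gives 0.042 by chi-square and 0.053 by Fisher.

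**Step 6: effect of an expected-count trigger.** Compared with the pooled reading, the placebo-excess tail falls from 4.17% to 2.03% (5% rate), 3.81% to 2.60% (10%) and 3.45% to 1.96% (20%). Power to flag a true estriol excess falls from 42.4% to 29.4% (30% v 5%) and from 24.3% to 17.5% (30% v 10%). On the per-arm reading, power in these two scenarios is unchanged.

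**The case against.** A reader might infer that the rule systematically flatters estriol. The documents do not support that. The one-sided pattern is confined to rarer events, up to about 12 of 60 women. Fisher is also lopsided at low rates (2.03% placebo excess against 0.00% estriol excess at a 5% rate), because 4:1 allocation and sparse events drive the asymmetry. Uncorrected chi-square never has less power than Fisher to flag estriol harm. Total two-sided error is 2.9-5.3% over the rates examined and below 5% at event rates up to 30%, so overall size is not materially inflated. All of this stands.

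The figures also depend on readings that the protocol leaves open. The 0.6 and the 1/48 versus 2/12 example need the pooled reading. With a continuity correction that table gives p = 0.18, and the pooled placebo-excess tail is 1.2-1.5%, so the inflation disappears. This stands as a limit on size, but it also shows that the rule does not fix which test is run.

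Finally, expected count below 5 is a rule of thumb, no decision rests on adverse-event p-values, the study calls itself exploratory, and section 8.2.1 leaves detailed methods to the SAP. That keeps the point minor. It does not remove it: the protocol states a specific trigger in two places, and the trigger is on the wrong quantity.

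**Conclusion.** The point holds as a fault in test selection, of minor weight. The trigger is an observed percentage with no denominator, and on each of the three readings examined it permits chi-square at expected placebo counts far below 5 (0.6, 0.8 or 1.2). If the test is uncorrected Pearson, some sparse-table p-values are too small, and the false placebo-excess tail reaches 4.2% (pooled) or 3.6% (per arm) against a nominal 2.5%.

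It does not show a general bias toward estriol or a material excess of two-sided error. The sizes rest on 48 and 12 treated women and equal event rates of 3-40%. If the 10 safety-phase women were added (56 and 14), the pooled minimum would be 4 × 14/70 = 0.8, which leaves the conclusion unchanged.

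**What to change.** In section 8.2.8 and in the Safety Analyses paragraph of the summary, replace the trigger with: Fisher's exact test whenever any expected cell count is below 5. Report each arm's incidence with an exact 95% confidence interval, so that interpretation rests on the estimates.

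The cost is one sentence in two places, with no new data or procedures. The price is sensitivity: against the pooled reading, the power losses in step 6 apply, while against the per-arm reading there is none in those scenarios. The text should therefore also say that a non-significant adverse-event p-value is not evidence of safety.
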